3.3 Special Populations

The following special populations are excluded from this study:

- Cognitively impaired adults/adults with impaired decision-making capacity
- Individuals who are not yet adults (infants, children, teenagers)
- Prisoners
- Pregnant women

3.4 Inclusion of Women and Minorities

Both men and women and members of all races and ethnic groups are eligible for this study

4.0 Local and Study-Wide Number of Subjects

A total of 41 participants will be accrued (with a maximum of n=27 evaluable for the primary endpoint) from multiple sites, including RPCI, will be enrolled. RPCI is expected to enroll 38 participants over a period of 5 years.

5.0 Local and Study-Wide Recruitment Methods

Participants will be identified/recruited/screened from patients at the GI clinic at RPCI and participating sites and from multi-disciplinary conference discussion.

6.0 Multi-Site Research

It is the responsibility of the principal Investigator to ensure that:

- All sites have the most current version of the protocol, consent document, and HIPAA authorization.
- All required approvals (initial, continuing review and modifications) have been obtained at each site (including approval by the site's IRB of record).
- All modifications have been communicated to sites, and approved (including approval by the site's IRB of record) before the modification is implemented.
- All engaged participating sites will safeguard data, including secure transmission of data, as required by local information security policies.
- All local site investigators will conduct the study in accordance with applicable federal regulations and local laws.
- All non-compliance with the study protocol or applicable requirements will be reported in accordance with local policy.

Refer to Appendix A: Instructions for Multi-Site Studies

7.0 Study Timelines

A maximum of 41 participants at multiple sites, including RPCI will be enrolled. Accrual is expected to take 5 years, with follow-up for 12 months from the start of combination therapy. Upon completion of the 12-month follow-up period, patient survival status will be monitored every 6 months.

8.0 Study Endpoints

- The primary endpoint is the Overall Response Rate (ORR), defined as partial or complete response (per irRECIST) within 6 months of initiating combination therapy.
- The secondary endpoint is time to tumor progression (TTP), measured from the date of

study enrollment to the first observation of progressive disease.

- Exploratory endpoints: Pre-treatment levels of immunosuppressive cells and the functional activity of effector T cells will be compared to post-treatment blood and tumor samples and will be correlated with overall survival.

9.0 Design

This is an open-label, single arm, non-randomized, multi-center Phase Ib/II study of sorafenib when administered with pembrolizumab in patients with advanced hepatocellular carcinoma. The study will include an initial Phase Ib safety lead-in cohort of 6 patients.

Prior to starting on the combination therapy of sorafenib + pembrolizumab, patients will have completed initial treatment with sorafenib alone and must be stable on sorafenib (at least 200 mg BID for a minimum of 1 week) before the introduction of pembrolizumab. The sorafenib starting dose will be at the discretion of the treating physician based on clinical assessment of the patient.

All participants will sign an informed consent prior to any study-related tests. All participants will meet the inclusion and exclusion criteria summarized in Section 3.1 and 3.2.

9.1 Phase Ib/II

The first 6 patients who have completed at least 4 weeks of sorafenib-only treatment and begin the combination therapy (addition of pembrolizumab at a fixed dose of 200 mg Q3W) will comprise the Phase 1b safety lead-in. Patients who withdraw from the study prior to initiation of combination therapy (for reasons other than DLT) will be replaced.

Definition of Dose-Limiting Toxicity: A dose-limiting toxicity will be defined as any \geq grade 3 clinically significant toxicity which is deemed possibly treatment related and occurs within the first cycle of combination therapy. Toxicity will be assessed according to the NCI Common Terminology Criteria for Adverse Events [Version 4.0 \(CTCAE v4.0\)](#).

Patient data for the safety lead-in portion of the study will be discussed and monitored by The Early Phase Clinical Trials committee, which meets on a regular basis per the RPCI Data Safety Monitoring Plan.

After a minimum of 6 have completed at least one cycle of sorafenib + pembrolizumab, the study will be suspended, and the safety/tolerability of the combination will be examined. At that time, the study team will decide what action to take, e.g., continue the study as is, make changes to the study with regard to treatment or dose modifications, or discontinue the study.

- If ≥ 2 of these patients experience an unexpected, treatment related toxicity of grade ≥ 3 during the first cycle of combination therapy, the study will be stopped to reevaluate dosing. We anticipate that such limiting toxicities will be observed in ≤ 1 of the first 6 patients. All evaluable patients who receive the Phase 2 dose of pembrolizumab (200 mg Q3W) will be included in the Phase 2 study.

Once analysis is complete and a safe treatment plan has been established, the Phase II study will commence.

Patients who have toxicity during the first 3 weeks of combination therapy that appears to be attributed to sorafenib will have sorafenib dose reduced to 2 x 200 mg every other day, as was done in the SHARP study(11). We anticipate such dose modifications to be infrequent. Patients will be considered evaluable if they receive more than 75% of prescribed sorafenib dosing during

Roswell Park Protocol No.: I 35316

the first 3 weeks of combination therapy (a medication diary will be provided during this time to monitor participant compliance: see Appendix F). All toxicities will be assessed upon completion of the first 6 evaluable patients to see if any higher than anticipated occurrence of sorafenib toxicity is seen due to the addition of pembrolizumab.

The goal of the study is to evaluate efficacy of the combination therapy, therefore patients who are removed from the study prior to receiving the soraf+pembro combination treatment will be replaced. This includes replacing patients who do not tolerate sorafenib alone, as administered in the 1st 4 - 6 weeks of the treatment regimen. In addition, the following patients will be replaced:

- Patient withdraws consent
- Withdrawal from study due to toxicity,
- Withdrawal from study due to liver failure
- Patients who withdraw before the Week 12 (± 1 week) response assessment (for reasons other than progression)

Patients who withdraw due to disease progression prior to the Week 12 (± 1 week) response assessment of the combination therapy will not be replaced and will be counted as non-responders in the response rate calculations.

Patients who complete the 4-6 week initial treatment with sorafenib alone, and withdraw from the study after being treated with the combination therapy will not be replaced and will be counted as non-responders in the response rate calculations.

Patients will receive sorafenib + pembrolizumab until progression. If a patient discontinues either agent due to toxicity, they will still be able to stay on study until progression. Clinical benefit will be considered when making decision to stop therapy as radiographic reflection of true failure of this combination is still unknown.

Disease assessment (imaging) will be done every 6 weeks from the start of C1D1 combination therapy, with a confirmatory assessment no less than 6 weeks after an irPR or irCR or irPD. Therapy will be continued until the confirmatory scan, even if progression is noted on the Week 12 scan. After the 12-week scan disease assessment will be done every 9 weeks (± 1 week). Note: Timing for assessing ORR in patients on immunotherapies is not clear. Disease stability is the commonly seen response to sorafenib alone. Allowing continuation until the confirmatory scan at Week 18, even if progression is seen, allows us to assess the true response to this novel combination.

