17.0 Safety Evaluation

17.1 Adverse Events

An adverse event or adverse experience (AE) is any untoward medical occurrence associated with the use of a drug in humans, whether or not considered drug related. Therefore, an AE can be ANY unfavorable and unintended sign (including an abnormal laboratory finding), symptom, or disease temporally associated with the use of a medicinal (investigational) product, whether or not considered related to the medicinal (investigational) product (attribution of ‘unrelated’, ‘unlikely’, ‘possible’, ‘probable’, or ‘definite’).

An AE is considered “unexpected” if it is not listed in the investigator brochure or is not listed at the specificity or severity that has been observed; or if an investigator brochure is not required or available, is not consistent with the risk information described in the general investigational plan in other study-related documents.

- **Diagnosis Versus Signs and Symptoms**

If known, a diagnosis should be recorded on the CRF rather than individual signs and symptoms (e.g., record only liver failure or hepatitis rather than jaundice, asterixis, and elevated transaminases). However, if a constellation of signs and/or symptoms cannot be clinically characterized as a single diagnosis or syndrome at the time of reporting, each individual event should be recorded as an AE or SAE on the CRF. If a diagnosis is subsequently established, it should be reported as follow-up information.

- **Adverse Events Occurring Secondary to Other Events**

In general, AEs occurring secondary to other events (e.g., cascade events or clinical sequelae) should be identified by their primary cause. For example, if severe diarrhea is known to have resulted in dehydration, it is sufficient to record only diarrhea as an AE or SAE on the CRF.

However, clinically significant AEs occurring secondary to an initiating event that are separated in time should be recorded as independent events on the CRF. For example, if a severe gastrointestinal hemorrhage leads to renal failure, both events should be recorded separately on the CRF.

- **Abnormal Laboratory Values**

Only clinically significant laboratory abnormalities that require active management will be recorded as AEs or SAEs on the CRF (e.g., abnormalities that require study drug dose modification, discontinuation of study treatment, more frequent follow-up assessments, further diagnostic investigation, etc.).

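### The lead-in's 2-of-6 rule does not count the DLT that section 9.1 defines: it counts unexpected events, so DLTs already listed in the brochure have no numeric trigger

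*Combined protocol and SAP*

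**What the plan says.** Section 9.1 starts with a six-patient safety lead-in. It defines a DLT as any toxicity of at least "grade 3 clinically significant toxicity which is deemed possibly treatment related and occurs within the first cycle of combination therapy". The definition has no expectedness condition.

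The numeric rule comes a few lines later. The study stops to re-evaluate dosing if at least 2 "of these patients experience an unexpected, treatment related toxicity of grade" 3 or higher in the first combination cycle. Section 19.1 repeats it, again limited to unexpected events. The following sentence begins "We anticipate that such limiting toxicities will be observed in" and expects at most one such patient in six, as if the counted events were the DLTs just defined.

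Section 17.1 calls an event unexpected "if it is not listed in the investigator brochure or is not listed at the specificity or severity that has been observed". Where no brochure is required or available, it falls back on the risk information in other study documents.

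The term DLT has one other use, in 9.1: "Patients who withdraw from the study prior to initiation of combination therapy (for reasons other than DLT) will be replaced".

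Separately from the rule, once six patients have completed a combination cycle, "the study will be suspended, and the safety/tolerability of the combination will be examined". The study team then chooses whether to continue, modify or stop. Section 9.1 adds: "Once analysis is complete and a safe treatment plan has been established, the Phase II study will commence".

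**The concern.** A safety lead-in normally has one event definition and one count. Here the defined event has no count, and the counted event has a different definition. Two people applying the plan to the same six patients could reach different answers on whether dosing must be re-evaluated.

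The difference matters because of what this lead-in is for. Sections 9.1 and 10.2 say toxicities will be assessed to see whether adding pembrolizumab raises sorafenib toxicity above what was anticipated. Section 2.4 notes that several serious immune-mediated events of pembrolizumab also occur with sorafenib. An excess of known, overlapping toxicity is thus a foreseeable signal, and an expectedness filter based on listing rather than frequency can leave it out. At stake is the pre-specified threshold for a mandatory dosing re-evaluation. The primary endpoint and the 4-of-27 rule are unaffected.

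**Working it through.** **1. The two events compared**

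| Element | DLT (9.1) | Event counted by the rule (9.1, 19.1) |
|---|---|---|
| Grade | 3 or higher | 3 or higher |
| Window | first combination cycle | first cycle (10.0 defines a cycle as combination therapy) |
| Relatedness | at least possibly related | treatment related, level not stated |
| Clinically significant | required | not mentioned |
| Unexpected | not mentioned | required |
| Numeric threshold | none | 2 or more of 6 |

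The expectedness condition narrows the count. Omitting clinical significance widens it. The relatedness wording could narrow it further, if *possible* on the 17.2 attribution scale is read as not enough. Neither event therefore contains the other.

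**2. The other use of DLT.** The replacement clause concerns patients who leave before combination therapy. A DLT can occur only during the first combination cycle, so that exception is empty.

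**3. What expectedness removes.** The case is clearest for pembrolizumab, the only drug whose brochure is cited (2.3). A grade 3 event listed there at that specificity and severity does not count. If it exceeds the listed severity, it does. For sorafenib the status is arguable: the study does not supply it (32.2), no brochure is cited, and 13.2 lists common reactions without grades.

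**4. Logical extreme, with no assumed rates.** If all six patients have DLTs and none is unexpected, the rule counts 0 of 6. It also stays silent if exactly one patient has an unexpected event.

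**5. Trigger probability.** The plan states no operating characteristic for this rule, so there is no figure to reproduce. With q the per-patient probability of a counted event:

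P(X ≥ 2) = 1 − (1 − q)^6 − 6q(1 − q)^5

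Counting DLTs as defined, q is the DLT rate. The rates below are assumed; the documents give none.

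| DLT rate | (1 − q)^6 | 6q(1 − q)^5 | P(2 or more of 6) |
|---|---|---|---|
| 10% | 0.5314 | 0.3543 | 11.4% |
| 20% | 0.2621 | 0.3932 | 34.5% |
| one third | 0.0878 | 0.2634 | 65% |
| 50% | 0.0156 | 0.0938 | 89% |

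Under the current wording, q is the chance that a patient has at least one unexpected treatment-related grade 3 or higher event. For assumed q of 2%, 5%, 10%, 15% and 20%, the same formula gives 0.6%, 3.3%, 11.4%, 22% and 34.5%.

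q is per patient, so a patient with several DLTs counts if any one is unexpected. As an illustration, take a DLT rate of one third, each DLT unexpected with probability 0.2, and k DLTs per affected patient. Then q = (1/3)(1 − 0.8^k). For k = 1, 2 and 3, q is 0.067, 0.120 and 0.163, and the trigger probability is 5.6%, 15.6% and 25.4%, against 65% if all DLTs counted.

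**The case against.** The strongest reply is that little is lost in practice. The study is suspended after six patients whatever the count, all toxicities are assessed, and the early-phase committee monitors the lead-in. Phase 1 reporting in 17.2 covers every grade and attribution regardless of expectedness. Individual rules also act: a patient with early toxicity attributed to sorafenib "will have sorafenib dose reduced to 2 x 200 mg every other day", and Appendices F, I and J govern holds and discontinuations. All of this stands. A reader might infer that the defined DLT can influence nothing, or that known toxicity escapes review. The documents do not support that, because the review can weigh any DLT. They provide no number by which it must act.

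The second reply is that the filter may be deliberate, to stop background sorafenib toxicity from tripping the rule. That is a sensible aim, but no exemption is stated and the DLT definition covers any qualifying toxicity. The aim can be met by naming the exempt events.

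The third is that 17.8 includes frequency in its meaning of unexpected, so an excess of listed events might count. Section 17.8 defines unanticipated problems for reporting. The adverse-event definition is in 17.1 and does not mention frequency.

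A reader might also infer that the counted event is simply a subset of DLTs, so that the current trigger probability cannot exceed the figures in the DLT table. That holds only for unexpected events that are also DLTs. An unexpected event judged not clinically significant would count under the rule without being a DLT. Section 17.1 largely closes that route for laboratory values, since only clinically significant abnormalities are recorded as adverse events, but states no such filter for other events.

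**Conclusion.** The point holds as a conflict between a definition and a rule, and it is worth fixing. No numeric rule uses the DLT of 9.1, and six of six patients could have brochure-listed DLTs without triggering the mandatory dosing re-evaluation. Whether dosing is re-evaluated would then rest on judgement without a threshold.

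The mismatch is certain from the text and needs no assumption. Its practical size is not known: it depends on the true DLT rate and on how many DLTs the brochure and label already list, and the documents give neither. The 11.4% to 89% range describes the rule if it counted DLTs, assuming independent patients with a common rate. These are chances of mandatory re-evaluation, not of a pause, because the pause occurs in every case.

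**What to change.** - In 9.1 and 19.1, state the rule as at least 2 of 6 patients with a DLT as defined in 9.1.
- If certain expected sorafenib toxicities are meant to be exempt, list them with their grades in the DLT definition.
- Add that any unexpected treatment-related grade 3 or higher toxicity also counts, so that the change does not impose a clinical-significance filter on unexpected events. Say which 17.2 attribution levels qualify as related.
- In 19.1, specify the first cycle of combination therapy, to match 9.1.
- State the trigger probabilities when DLTs are counted: 11.4%, 34.5%, 65% and 89% at assumed DLT rates of 10%, 20%, one third and 50%. With exemptions, the rate is that of non-exempt DLTs. If unexpected events outside the DLT definition also count, these figures are minimums.

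The change is wording in two sections, with no added patients or visits. The downside is more frequent mandatory re-evaluation, including for known sorafenib toxicity unless exempted: 11.4% of the time at a 10% DLT rate and 34.5% at 20%. It would fall within the suspension already planned after six patients.

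### The lead-in check for added sorafenib toxicity can pass over patients whose sorafenib was held, cut or stopped for toxicity, because evaluability has no toxicity exception and its dose denominator is undefined

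*Combined protocol and SAP*

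**What the plan says.** All of the following is in Section 9.1 of the combined protocol and SAP unless noted.

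- **The check.** "All toxicities will be assessed upon completion of the first 6 evaluable patients to see if any higher than anticipated occurrence of sorafenib toxicity" arises once pembrolizumab is added. Section 10.2 repeats it, also for the first six evaluable patients.
- **Evaluability.** "Patients will be considered evaluable if they receive more than 75% of prescribed sorafenib dosing during" the first three weeks of combination therapy. A medication diary tracks compliance over that time. The plan does not define the prescribed amount and makes no exception for toxicity.
- **DLT.** A grade 3 or higher "clinically significant toxicity which is deemed possibly treatment related and occurs within the first cycle of combination therapy". Section 10.0 sets a cycle at three weeks, so the DLT and evaluability windows are the same 21 days.
- **Dose rules in that window.** Patients with toxicity attributed to sorafenib "will have sorafenib dose reduced to 2 x 200 mg every other day". Appendix I interrupts sorafenib for grade 3 skin toxicity, and Section 10.1.2 discontinues it for unexplained, significant transaminase rises.
- **Staying on study.** "If a patient discontinues either agent due to toxicity, they will still be able to stay on study until progression".
- **The only DLT exception to replacement.** "Patients who withdraw from the study prior to initiation of combination therapy (for reasons other than DLT) will be replaced".
- **Stopping rule.** The study stops to re-evaluate dosing if two or more of the first six "experience an unexpected, treatment related toxicity of grade" 3 or higher in the first combination cycle. The lead-in six are the first who complete at least four weeks of sorafenib alone and begin the combination. Section 19.1 restates the rule.
- **Suspension review.** "After a minimum of 6 have completed at least one cycle of sorafenib + pembrolizumab, the study will be suspended", and safety and tolerability are then examined.

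**The concern.** A set used to look for toxicity should not be selected on tolerance of the drug. Here the evaluability threshold runs over the same 21 days as the toxicity being looked for, and the plan's own dose rules can push a patient with toxicity below it. A patient who stops sorafenib for toxicity may stay on study and so is not a withdrawal; evaluability alone then decides whether that patient is among the six. The DLT exception does not help. It applies to withdrawal before the combination starts, when a DLT as defined cannot yet occur.

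This check matters because the stopping rule counts only unexpected events, which Section 17.1 defines against the investigator brochure. Where the sorafenib reactions listed in Section 13.2 are expected at the severity seen, they do not count toward that rule. Apart from the general suspension review, this check is then the plan's stated means of finding an excess of them.

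**Working it through.** The documents give no operating characteristics for the lead-in, so there is no stated figure to reproduce. The check has two steps: when a patient drops to 75% or below, and how often that could touch a group of six.

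**Inputs.** Window of 21 days (Sections 9.1 and 10.0). Starting dose 800 mg/day recommended, 400 mg/day minimum (Section 10.1). Reduced dose 400 mg every other day (Section 9.1), or 400 mg daily as an Appendix I option. Threshold: strictly more than 75%.

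**Step 1: share of dose received, taking prescribed as the C1D1 dose.** Share = mg taken / (21 × starting daily dose). The denominator is 21 × 800 = 16,800 mg or 21 × 400 = 8,400 mg.

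| Event | Calculation | Share | Evaluable? |
|---|---|---|---|
| Hold of 5 days | 16/21 | 76.2% | yes |
| Hold of 6 days | 15/21 | 71.4% | no |
| Stop on day 16 | 15/21 | 71.4% | no |
| Stop on day 17 | 16/21 | 76.2% | yes |
| 800 daily to 400 alternate days, from day 14 | (13×800 + 4×400)/16,800 | 71.4% | no |
| Same, from day 15, first reduced dose day 15 | (14×800 + 4×400)/16,800 | 76.2% | yes |
| Same, from day 15, first reduced dose day 16 | (14×800 + 3×400)/16,800 | 73.8% | no |
| Same, from day 16 | (15×800 + 3×400)/16,800 | 78.6% | yes |
| 400 daily to 400 alternate days, from day 10 | (9×400 + 6×400)/8,400 | 71.4% | no |
| Same, from day 12 | (11×400 + 5×400)/8,400 | 76.2% | yes |
| 800 daily to 400 daily, from day 11 | (10×800 + 11×400)/16,800 | 73.8% | no |
| Same, from day 12 | (11×800 + 10×400)/16,800 | 76.2% | yes |

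From 400 mg/day, a change on day 11 gives 76.2% or 71.4%, depending on which day the first reduced dose falls.

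**Step 2: the same patients with prescribed taken as the current dose.** A compliant patient on a reduced dose has taken 100% and stays in. A held patient stays in if held days are not counted as prescribed days. If held days are counted, a 6-day hold still gives 71.4%. The diary in Appendix D asks patients to record a changed dose, but no text says whether the denominator changes with it.

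**Step 3: how often six patients would be touched.** Let *q* be the share of combination starters who fall to 75% or below because of toxicity. The documents do not give *q*; I assume 5% to 30%. The chance that the first six starters include at least one such patient is 1 − (1 − *q*)^6:

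- *q* = 5%: 1 − 0.95^6 = 26%
- *q* = 10%: 1 − 0.90^6 = 47%
- *q* = 20%: 1 − 0.80^6 = 74%
- *q* = 30%: 1 − 0.70^6 = 88%

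If the check is confined to six evaluable patients, it contains none of them by construction. Section 9.1 expects sorafenib dose modifications to be infrequent, so the lower values fit the plan's own expectation better.

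**The case against.** The strongest reply is that the sentence sets a time and not an analysis set. It speaks of all toxicities, assessed upon completion of six evaluable patients. Read that way, a non-evaluable patient delays the check and adds data, and nobody is removed. A second reply is that the diary's stated purpose is compliance, which is naturally judged against the dose currently ordered; compliant reduced patients then stay in. Both readings are reasonable and the text rules out neither. Nor does it say that toxicities in non-evaluable patients are included, or that the denominator follows a reduction. The ambiguity therefore stands.

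A reader might infer that the stopping rule itself loses sensitivity. The documents do not support that. The rule is attached to the first six patients who begin the combination, with no mention of evaluability. The sorafenib check has no threshold of its own, so it has no stopping probability to degrade.

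A reader might also infer that safety oversight is lost. It is not. Section 17.2 requires routine Phase 1 reporting of Grade 1 to 4 events at every attribution, the early-phase committee monitors the lead-in (Sections 9.1 and 20.0), and the suspension review is broad enough to cover known sorafenib reactions. That review is, however, triggered by patients who complete a cycle, and does not say how those who stop early are handled.

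Finally, how far known reactions fall outside the stopping rule depends on the investigator brochure, which is not among the documents. A known reaction above its listed severity could still count.

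**Conclusion.** The point holds in a limited form. The written rule allows the check for added sorafenib toxicity to be made on patients selected for having tolerated sorafenib, and nothing in the text prevents it. This requires two readings together: that prescribed means the C1D1 dose, and that the check is confined to evaluable patients. Under both, a toxicity hold of 6 or more days, a stop by day 16, or a cut from 800 mg/day to 400 mg every other day by day 14 leaves 71.4% or less and takes the patient out of the six. Under the timing-only reading this does not happen; under the current-dose reading it happens less or not at all.

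The dose thresholds are exact under the C1D1 reading. The 26% to 88% range rests on an assumed *q* and only shows that one exclusion among six is not remote. It does not measure harm to any decision. What is weakened is one planned check, and it is worth correcting because the correction is short.

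**What to change.** In Sections 9.1 and 10.2:

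1. State that any patient who receives pembrolizumab and has a DLT, or a toxicity-driven hold, reduction or stop of either drug in combination cycle 1, is evaluable for the lead-in safety assessment and is not replaced in it.
2. Apply the more-than-75% rule only to shortfalls not caused by toxicity, and measure it against the C1D1 dose.
3. Attach the exception for DLT to withdrawals during combination cycle 1.

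If the lead-in has already been reviewed, re-tabulate it on this set.

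The cost is wording, with no new patients, visits or tests. The downside is a somewhat higher chance of pausing a tolerable regimen. If the stopping rule is already applied to the first six starters, that chance is essentially unchanged. If a team had been applying it to evaluable patients, the size can be illustrated with assumed values. At a true event rate *p* = 10% with all affected patients kept, P(at least 2 of 6) = 1 − 0.9^6 − 6 × 0.1 × 0.9^5 = 11.4%. If half of the affected patients leave the six, the effective rate is 0.10 × 0.5 / (1 − 0.10 × 0.5) = 5.3%, and the same formula gives 3.6%.
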